### 8.2.5.3 Summary of Baseline Characteristics, Demographics, and Other Analyses

## Demographic and Baseline Characteristics

The comparability of the treatment groups for each relevant characteristic will be assessed by the use of tables and/or graphs. No statistical hypothesis tests will be performed on these characteristics. The number and percentage of patients screened, randomized, the primary reasons for screening failure, and the primary reason for discontinuation will be displayed. Demographic variables, baseline characteristics, primary and secondary diagnoses, and prior and concomitant therapies will be summarized by treatment either by descriptive statistics or categorical tables.

### 8.2.6 Multiplicity

No multiplicity adjustment is necessary since no hypothesis is tested in this study.

### 8.2.7 Sample Size and Power Calculations

This study initially planned to enroll a total of 90 subjects, but due to the modification in protocol such as inclusion and exclusion criteria, an additional 90 subjects will be enrolled as

cohort 2 [redacted]

[redacted]. The cohort 2 will enroll subjects as initially planned for this protocol as follows:

The target number of subjects for the safety analyses will be 90 subjects (MK-5592 treatment arm: 60 subjects, Voriconazole treatment arm: 30 subjects) in this study. From past experiences of the sponsor as well as information of competitors a total number of 90 subjects were set as a target number with consideration of recruitment feasibility.

A total of 90 subjects include subjects with invasive aspergillosis and chronic pulmonary aspergillosis (chronic progressive pulmonary aspergillosis and simple pulmonary aspergilloma). In order to obtain MK-5592 data as much as possible with a limitation of the sample size, the allocation ratio was set 2 to 1. 15 subjects with invasive aspergillosis as a target number will be enrolled. Fusariosis and zygomycosis are very rare deep-seated fungal infections and it is reported that Voriconazole is not effective for treatment of zygomycosis, so subjects with those infections will not be randomized and will be enrolled in the MK-5592 treatment arm without a target number of enrollment.

According to clinical database of Posaconazole Oral Suspension, which is approved and available in the markets of Europe and the United States, as well as clinical studies of MK-5592 in the new formulations up to date, the incident rates of frequently observed adverse experiences (pyrexia, diarrhea, nausea, headache, vomiting and cough) are expected to be approximately 10% - 20%. Assuming that incident rates of the MK-5592 arm and Voriconazole arm are comparable, the half-width of the 95% confidence interval for the difference of the incidence rates will be 14.6% - 17.9% with 60 subjects of the MK-5922 arm and 30 subjects of the Voriconazole arm (Table 28). If a particular adverse experience is not observed in any of the 60 patients in the MK-5592 treatment arm, the true incidence rate for the particular adverse experience is less than 2.6% with 80% confidence. For efficacy assessment, assuming that response rate of 60% (80%), the lower limits of confidence interval for MK-5922 arm will be 46.5% (67.7%) with the sample size of 60.

Table 28 95% Confidence Interval for Difference of the Incidence Rates for Adverse Events

Incident Rates for both arms (difference of 0%)	95% Confidence Interval		
	Lower Bound	Upper Bound	A half-width of the 95% CI
10%	-12.5	16.8	14.6%
15%	-15.9	16.4	16.1%
20%	-16.3	19.5	17.9%

Incidence Rates for the MK-5592 and Voriconazole treatment arm are assumed to be equal.  
(MK-5592: 60 subjects, Voriconazole: 30 subjects)  
95% confidence interval was calculated with the Miettinen and Nurminen method.

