### 3.2 Secondary Objective(s) & Hypothesis(es)

- 1) Objective: To assess the overall response on Day 42 of MK-5592 and Voriconazole in Japanese subjects with Invasive aspergillosis.
- 2) Objective: To assess the overall response on Day 84 of MK-5592 and Voriconazole in Japanese subjects with Chronic pulmonary aspergillosis (chronic progressive pulmonary aspergillosis and simple pulmonary aspergilloma)

- 3) Objective: To assess the overall response at EOT of MK-5592 and Voriconazole in Japanese subjects with Aspergillosis [Invasive aspergillosis or Chronic pulmonary aspergillosis (Chronic progressive pulmonary aspergillosis and simple pulmonary aspergilloma)]
- 4) Objective: To assess the safety and efficacy of MK-5592 in Japanese subjects with fusariosis and zygomycosis
- 5) Objective: To assess the pharmacokinetic profile of MK-5592 in Japanese subjects with deep-seated fungal infection.

An overall response criterion is defined in Section 4.2.3.1. Also, all objectives in Section 3 will be performed for Cohort 2 only.

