#### **8.1.1 Efficacy Analyses**

The primary endpoints, primary analysis population, and statistical method that will be employed for the efficacy analyses are presented in [Table 24](#) below.

The primary efficacy endpoint is the overall response assessed by CAC. The overall response rates (the proportion of subjects with “success” assessment [see Section 8.2.3.3]) for invasive aspergillosis at Day 42 and for chronic pulmonary aspergillosis (chronic progressive pulmonary aspergillosis and simple pulmonary aspergilloma) at Day 84 and their 95% confidence intervals will be computed by treatment. Subjects with solid oral tablet, IV solution and switch from IV solution to solid oral tablet for the MK-5592 treatment arm will

be pooled for the analyses due to the fact that it reflects clinical practice and the different routes of administration achieve targeted plasma concentration level of MK-5592. Likewise, subjects with oral tablet, IV solution and switch from IV solution to oral tablet for the Voriconazole treatment arm will be pooled for the analyses.

The overall response for the subjects with fusariosis and zygomycosis will be listed for MK-5592 treatment arm since the enrollment of these infections will be very limited.

Table 24 Analysis Strategy for Primary Efficacy Endpoint

Endpoint/Variable (Description, Timepoint)	Statistical Method	Analysis Population	Missing Data Approach
Overall response rates for invasive aspergillosis at Day 42 and for chronic pulmonary aspergillosis at Day 84	95% CI with Clopper-Pearson Exact Method	FAS	Carry Forward

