### 8.1.3 Power and Sample Size

This study initially planned to enroll a total of 90 subjects but due to the modification in protocol such as inclusion and exclusion criteria, an additional 90 subjects will be enrolled as cohort 2, [REDACTED] The cohort 2 will enroll subjects as initially planned for this protocol:

This study will randomize 60 subjects into the MK-5592 treatment arm and 30 into the Voriconazole treatment arm. A total number of 90 subjects were set with consideration of recruitment feasibility based on the past experiences (See Section 8.2.7 for details). A total of 90 subjects include those with all aspergillosis for safety analyses, and among them 15 subjects with invasive aspergillosis as a target number will be enrolled. Subjects with fusariosis and zygomycosis will be assigned to the MK-5592 treatment arm and their target number of recruitment is not set.

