#### **8.2.5 Statistical Methods**

The main objective of this study is assessment of safety and the formal hypothesis testing for efficacy endpoints will not be conducted. Nominal p-values and confidence intervals will be presented at the  $\alpha=0.05$  (2-sided) level.

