##### **8.2.5.1 Statistical Methods for Efficacy**

###### **8.2.5.1.1 Primary Efficacy Analysis**

The primary efficacy endpoint is the overall response assessed by CAC. The overall response rates (the proportion of subjects with “success” assessment) for invasive aspergillosis at Day 42 and for chronic pulmonary aspergillosis (chronic progressive pulmonary aspergillosis and simple pulmonary aspergilloma) at Day 84 and their 95% confidence intervals will be computed by treatment. Subjects with solid oral tablet, IV solution and switch from IV solution to solid oral tablet for the MK-5592 treatment arm will be pooled for the analyses due to the fact that it reflects clinical practice and the different routes of administration achieve targeted plasma concentration level of MK-5592. Likewise, subjects with oral tablet, IV solution and switch from IV solution to oral tablet for the Voriconazole treatment arm will be pooled for the analyses. The 95% confidence intervals will be estimated with the Clopper-Pearson method.

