### 8.2.5.1.2 Secondary Efficacy Analysis

The overall response rates for invasive aspergillosis at Day 84 and for chronic pulmonary aspergillosis (chronic progressive pulmonary aspergillosis and simple pulmonary aspergilloma) at Day 42 will be provided by treatment ([Table 26](#)).

The overall response rate for all aspergillosis (invasive aspergillosis and chronic pulmonary aspergillosis are pooled) at EOT will be provided by treatment.

Clinical, radiological and mycological response rates for invasive aspergillosis and for chronic pulmonary aspergillosis (chronic progressive pulmonary aspergillosis and simple pulmonary aspergilloma) at Day 42 and Day 84 will be provided by treatment.

The overall response for the subjects with fusariosis and zygomycosis will be listed for MK-5592 treatment arm since the enrollment of these infections will be very limited.

As a sensitivity analysis, the overall response rates for invasive aspergillosis at Day 42 and for chronic pulmonary aspergillosis at Day 84 will be provided by treatment in the PP population. For the PP analysis, a subject with missing post-treatment response data or with 'unable to determine' response will be excluded. In addition, the overall response rates will be provided in the ITT population and also the overall response rates by investigators/sub-investigators will be provided in the FAS population.

Table 26 Analysis Strategy for Key Efficacy Variables

Endpoint/Variable (Description, Time Point)	Primary vs. Supportive Approach	Statistical Methods	Analysis Population	Missing Data Approach
Primary				
Overall response rates for invasive aspergillosis at Day 42 and for chronic pulmonary aspergillosis at Day 84	P	95% CI with Clopper-Pearson Exact Method	FAS	CF †
	S	Point Estimate	PP	CF †
	S	Point Estimate	ITT	CF †
	S	Point Estimate: Assessment by investigators/sub-investigators	FAS	CF †
Secondary				
Overall response rates for invasive aspergillosis at Day 84 and for chronic pulmonary aspergillosis at Day 42	P	Point Estimate	FAS	CF †
Overall response rate for all aspergillosis at EOT (invasive aspergillosis and chronic pulmonary aspergillosis are pooled)	P	Point Estimate	FAS	CF †
Clinical response rates, radiological response rates and mycological response rates for invasive aspergillosis and for chronic pulmonary aspergillosis at Day 42 and Day 84	P	Point Estimate	FAS	CF †

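### Section 8.2.7 states efficacy precision only for an MK-5592 arm of 60 that pools both diseases, while the visible primary intervals are by disease; the difference is material only for invasive aspergillosis

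*Combined protocol and SAP*

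**What the plan says.** Section 8.2.7 plans 90 aspergillosis subjects, 60 on MK-5592 and 30 on voriconazole, and says that the 90 cover both IA and CPA. Its one efficacy precision statement assumes response rates of 60% and 80% and reports that "the lower limits of confidence interval for MK-5922 arm will be 46.5% (67.7%) with the sample size of 60" (the drug code in that sentence is taken to mean MK-5592).

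The primary efficacy analysis is laid out by disease. Table 24 in section 8.1.1 lists "Overall response rates for invasive aspergillosis at Day 42 and for chronic pulmonary aspergillosis at Day 84", with a Clopper-Pearson interval in the FAS. Section 8.2.5.1.1 says of the two rates, the second being CPA "at Day 84 and their 95% confidence intervals will be computed by treatment". Section 3.2 has two separate objectives: "To assess the overall response on Day 42 of MK-5592 and Voriconazole in Japanese subjects with Invasive aspergillosis", and "To assess the overall response on Day 84 of MK-5592 and Voriconazole in Japanese subjects with Chronic pulmonary aspergillosis".

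Section 8.1.3 says of the 90 that "among them 15 subjects with invasive aspergillosis as a target number will be enrolled". Section 5.4 randomizes 2:1 within each disease-status category.

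The only rate described as pooled over the two diseases is a secondary one in Table 26: "Overall response rate for all aspergillosis at EOT (invasive aspergillosis and chronic pulmonary aspergillosis are pooled)". Its listed method is a point estimate.

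**The concern.** Section 8.2.2 sets no hypothesis, so stated precision is all the plan offers on what the efficacy data can show. The one figure given belongs to neither primary rate. A reader who carries it over to IA would expect a lower limit near 46% from data that, at the same 60% response, support about 26%. IA is also the rate meant for use beyond this trial: section 4.2.3 sets its time point at Day 42 to match the global 069 study, so that efficacy can be confirmed between the two.

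A smaller point lies in the same section. Table 28 is headed as equal rates in both arms, yet its 15% row does not look like an interval for a zero difference, since 15% of 30 is not a whole number of subjects.

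**Working it through.** **Inputs**
- Interval: two-sided 95% Clopper-Pearson, by treatment (section 8.2.5.1.1).
- Response rates: 60% and 80% (section 8.2.7).
- MK-5592 arm: 60 of 90 (section 8.2.7).
- IA target: 15 of the 90 (sections 8.1.3 and 8.2.7).
- Allocation: 2:1 within disease category (section 5.4).

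**Formula.** With x responders among n, the lower limit is the 0.025 quantile of Beta(x, n − x + 1) and the upper limit is the 0.975 quantile of Beta(x + 1, n − x).

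**Step 1: the plan's own figures (n = 60)**
- 36/60: 46.54% to 72.44%, width 25.9 points.
- 48/60: 67.67% to 89.22%, width 21.5 points.

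These round to the stated 46.5% and 67.7%.

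**Step 2: the split by disease on MK-5592**
- IA: 15 × 2/3 = 10.
- CPA: 60 − 10 = 50.

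**Step 3: intervals at those sizes**

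| MK-5592 arm | 60% response | 80% response |
|---|---|---|
| Pooled, n = 60 | 46.54 to 72.44 | 67.67 to 89.22 |
| CPA, n = 50 (30/50; 40/50) | 45.18 to 73.59 | 66.28 to 89.97 |
| IA, n = 10 (6/10; 8/10) | 26.24 to 87.84 | 44.39 to 97.48 |

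Gaps in the lower limit from n = 60:
- IA: 46.54 − 26.24 = 20.30 points, and 67.67 − 44.39 = 23.28 points.
- CPA: 46.54 − 45.18 = 1.36 points, and 67.67 − 66.28 = 1.39 points.

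At 60% response the IA interval is about 62 points wide, against 26 at n = 60.

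**Step 4: FAS exclusions.** Section 8.2.4.1 keeps only disease confirmed as proven or probable by the adjudication committee, and possible IA must be upgraded within 7 days of randomization. The documents give no exclusion rate, so these ranges are assumptions.
- IA, 5 to 10 subjects: lower limits 14.7% to 26.2% at 60% response, and 28.4% to 44.4% at 80%. The ends are 3/5 and 6/10, and 4/5 and 8/10.
- CPA, 45 to 50 subjects: 44.3% to 45.2%, and 65.4% to 66.3%. At 40 subjects: 43.3% and 64.4%, at most 3.3 points below the stated limits.

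**Step 5: Table 28 (minor).** The Miettinen-Nurminen interval holds every difference d for which |p̂₁ − p̂₂ − d| is at most 1.96 standard errors. The variance is evaluated at the maximum-likelihood rates constrained to differ by d, times N/(N − 1). With voriconazole minus MK-5592:

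| Counts (voriconazole v MK-5592) | Interval, points | Half-width | Table 28 |
|---|---|---|---|
| 3/30 v 6/60 | −12.46, 16.77 | 14.62 | 10% row matches |
| 4/30 v 9/60 | −15.87, 16.36 | 16.11 | 15% row matches |
| 5/30 v 9/60 | −13.26, 20.28 | 16.77 | no match |
| 6/30 v 12/60 | −16.27, 19.50 | 17.89 | 20% row matches |

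The 15% row is therefore 13.3% (4/30) against 15.0% (9/60), not equal rates. The table does not state the direction of subtraction.

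**The case against.** The strongest reply is that nothing in the sentence is false. It names its arm and its n, its limits are exact, and it does not claim to describe either primary rate. The same section tells the reader that the 90 include both diseases, that allocation is 2:1 and that 15 IA subjects are sought, so the pooled basis is disclosed. The sample size was set for safety and feasibility, and nothing is tested. All of this stands. It rules out calling the figures an arithmetic error. It does not remove the gap, because the reader must still derive the IA precision, and the one figure on offer points the wrong way.

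A second reply is that n=60 fits the pooled end-of-treatment rate. Table 26 lists that rate as a point estimate, but section 8.2.5 says in general that "Nominal p-values and confidence intervals will be presented", and section 8.2.5.1.3 is blacked out. So a reader should not infer that a pooled interval is absent from the plan. It remains true that the primary intervals in view are not pooled. One could read the primary endpoint as a single composite rate, but the plural wording, the separate objectives and the explicit mention of pooling only for the end-of-treatment rate all favour separate intervals.

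A third reply is that 10 and 50 are derived, not stated. That also stands. Sections 2.1 and 5.3 mention the target of about 15 IA subjects beside the total of 112; if cohort 1 subjects counted towards it, cohort 2 would have fewer IA subjects and the IA interval would be wider still.

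On Table 28, the counts are inferred by back-calculation, so the sponsor has to confirm them.

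**Conclusion.** The point holds as a mismatch between the precision stated and the primary analysis described. The limits in section 8.2.7 are right for a rate pooled over 60 subjects. Taken as the precision of the primary IA rate, they are about 20 points too high at 60% response and 23 points too high at 80%. For CPA the difference is 1.4 points and can be ignored.

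This rests on separate intervals by disease, on 15 IA subjects within the 90, and on 2:1 allocation within disease category. Losses from the FAS would widen the IA interval.

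A reader might infer that the plan miscalculated, or that the trial is too small for its efficacy aims. The documents support neither: the figures reproduce, no hypothesis is set, and the sample size was chosen for the safety analyses and feasibility.

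The Table 28 point is minor and separate. The half-width in the 15% row would be 16.8% with 5/30 instead of 16.1%, and the 14.6% to 17.9% range cited in section 8.2.7 comes from the other two rows and does not change.

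**What to change.** In section 8.2.7, restate the efficacy sentence. Suggested content: at response rates of 60% (80%), the Clopper-Pearson lower limits for MK-5592 are about 26.2% (44.4%) for IA with about 10 subjects and about 45.2% (66.3%) for CPA with about 50, both approximate and before FAS exclusions; the limits of 46.5% (67.7%) at n=60 apply only to a rate pooled over both diseases.

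For Table 28, the sponsor should confirm the counts behind the 15% row. It should then either relabel the row as 4/30 against 9/60 or recompute it, and should state that differences are voriconazole minus MK-5592.

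The cost is one sentence and one table row or footnote. Sample size, endpoints and analyses stay as they are.

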### **8.2.8 Subgroup Analyses and Effect of Baseline Factors**

To determine whether the treatment effect is consistent across various subgroups, the treatment effect for the primary endpoint will be estimated by the disease category in the following factors:

- Sex (female, male)
- Age (<65 vs.  $\geq$ 65 years)
- Weight (<60,  $\geq$ 60 kg)
- Fungal species
- Route of administration (oral, IV, switch)
- Diagnosis (proven, probable)

### **8.2.9 Interim Analysis**

Formal interim analyses are not planned in this study. Safety and PK data will be reviewed by the sponsor on an ongoing basis. No alpha adjustment is needed since no hypothesis is tested in this study.

### **8.2.10 Compliance (Medication Adherence)**

In this study, as part of the routine recording of the amount of study treatment taken by each patient, the volume of injection and the number of tablets remaining in study packaging will be counted, reviewed, and recorded at regular intervals. These results will be used to calculate patient compliance.

#### **8.2.10.1 IV Route**

Drug accountability data for MK-5592 and Voriconazole will be collected during the study. Compliance with protocol-directed MK-5592 and Voriconazole will be measured by patients: (1) receiving unscheduled study agent infusions, (2) missing an infusion, (3) receiving incorrect study agent dose, and (4) receiving an infusion at rate greater than a rate specified in the protocol. Numbers and percentages of patients with any deviation in these measures will be reported by treatment for the FAS and ASaT population.

Compliance will be assessed using the off-drug therapy records. On each day, each patient should take a certain infusion dosage. The compliance rate for each patient will be computed as follows:

$$\text{Percent Compliance} = \frac{\text{Number of Days on Therapy}}{\text{Number of Days Should be on Therapy}} \times 100.$$

Study period is defined as the number of days that the patient has been in the active treatment phase of the trial.

### **8.2.10.2 Oral Therapy**

A day within the study will be considered an “On-Therapy” day if the patient takes the required number of tablets. For a patient who is followed for the entire study period, the “Number of Days Should be on Therapy” is the total number of days from randomization to the last scheduled day for treatment administration for that patient. For a patient who discontinued from the study permanently, the “Number of Days Should be on Therapy” is the total number of days from randomization to the earlier/later date of the last dose of study medication.

For each patient, percent compliance will then be calculated using the following formula:

$$\text{Percent Compliance} = \frac{\text{Number of Days on Therapy}}{\text{Number of Days Should be on Therapy}} \times 100.$$

Summary statistics will be provided on percent compliance by treatment group for the FAS and ASaT.

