### 5.2.1.1.2 MK-5592 Solid Oral Tablet

**Table 16** provides the dosing of MK-5592 for subjects randomized to the MK-5592 treatment arm if on oral therapy.

MK-5592 oral tablet will be given every 12 hours on Day 1, with being not less than 9 hours or no more than 15 hours apart, and will be given once daily at approximately the same time every day with 24 hours apart on or after Day 2, with doses being not less than 21 hours or no more than 27 hours apart (doses on Day 2 should not be less than 9 hours or no more than 15 hours apart). MK-5592 solid oral tablet can be administered with or without the food, investigator instructs that all cases should be properly documented in the administration diary (dosage amount, and food intake data within 2 hours before or within 1 hour after taking study drug etc.).

If the dosing of study medication is delayed, the dose should be taken as soon as possible. Regarding the dose on or after Day 2, if it is more than 12 hours since the missed dose, the missed dose should be skipped and the next dose should be administered at the regularly scheduled time. If a subject vomits within 15 minutes of MK-5592 solid oral administration, the dosing should be repeated as soon as possible, following appropriate antiemetic treatment. Any missed doses should be properly documented in the subject's source documentation and eCRF.

Exceptionally, first dose could be in the night on Day 1. In case that the first dose is in the night, second dose could be in the morning on Day 2 approximately 12 hours apart from the first dose, third dose could be in the night on Day 2 approximately 12 hours apart from the second dose, and following doses from Day 3 could be in the night at approximately the same time every day with 24 hours apart with dosing being not less than 21 hours or no more than 27 hours apart. Also, if the dosing time need to be changed due to subject's schedule or operational handling (e.g., from QD dosing in pm to QD dosing in am), the dosing time could be adjusted within the range of allowance (scheduled time -/+3 hours). However, approximate dosing time needs to be fixed by Day 5 (e.g. QD dosing is done at approximately 9:00am every day from Day 5).

Table 16 Dosing for MK-5592 Oral Therapy for Cohort 2

	Day 1	Day 2-84
Dose	300 mg(3 tablets) BID	300 mg(3 tablets) QD

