#### 5.2.1.1.4 Voriconazole Oral Tablet

Table 18 provides the dosing of voriconazole for subjects randomized to the Voriconazole treatment arm if on oral therapy.

Voriconazole tablets will be administered as a 300 mg dose BID on Day 1 (approximately 12 hour intervals with being not less than 9 hours or no more than 15 hours apart) and followed by 200 mg dose BID (at approximately the same time every day with approximately 12 hour intervals being not less than 9 hours or no more than 15 hours apart). Voriconazole oral tablets SHOULD NOT BE TAKEN WITH A MEAL, and all cases should be taken at least one hour before or one hour following a meal. Investigator should instruct subject that all doses should be properly documented in the administration diary (dosage amount, and food intake data within 1 hour before or within 1 hour after taking study drug etc.). If the dosing of study medication is delayed, the dose should be taken as soon as possible at least one hour before or one hour following a meal. If it is more than 6 hours since the missed dose, the missed dose should be skipped and the next dose should be administered at the regularly scheduled time.

If a subject vomits within 15 minutes of Voriconazole oral administration, the dosing should be repeated as soon as possible, following appropriate antiemetic treatment. Any missed doses should be properly documented in the subject's source documentation and eCRF.

Exceptionally, first dose could be in the night on Day 1. In case that the first dose is in the night, second dose could be in the morning on Day 2 approximately 12 hours apart from the first dose, third dose could be in the night on Day 2 approximately 12 hours apart from the second dose, and following BID doses from Day 3 could be in the morning and night at approximately the same time every day with 12 hours apart with dosing being not less than 9 hours or no more than 15 hours apart. Also, if the dosing time need to be changed due to subject's schedule or operational handling, the dosing time could be adjusted within the range of allowance (scheduled time -/+3 hours). However, approximate dosing time needs to be fixed by Day 5.

Table 18 Dosing for Voriconazole Oral Tablet

	Day 1	Day 2-84*
Dose	300 mg (6 tablets) BID	200 mg (4 tablets) BID

\* : Dose adjustment may be performed based on the trough concentration of voriconazole.

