### 5.2.1.3 Treatment Duration

As a general rule, the treatment duration of all diseases is 84 days (77-84 days with considering the final treatment allowance). [However, for the subjects with zygomycosis, restart of the study therapy after finishing 84 day maximum treatment period or extension of treatment period could be done under the extension period with the prior approval from the Sponsor and obtaining the signing of a new informed consent from the only subject who have responded to the study therapy without intolerant toxicity if the investigator thinks that continuation of MK-5592 therapy would benefit the subjects with ample consideration of the MK-5592 profile and no alternative treatment in Japan (e.g. failure or intolerant to amphotericin B formulation). In addition to the above, in case of restart of the study therapy after the finishing 84 days, it can be done for the only subjects with same zygomycosis episode from the main study therapy (not new episode). The switch of the formulation (iv $\leftrightarrow$ tablet) could be done based on the subject's condition during the extension period but dose modification of MK-5592 must not be allowed. However, the study therapy must be discontinued when MK-5592 is marketed or the development of MK-5592 is discontinued in Japan. As a general rule, study medication information and adverse events are recorded (routine safety laboratory should be also monitored and recorded in the source document) during the study treatment over 84 days but refer to the specific procedure relating this matter including the details of information that should be recorded in CRF.] However, the treatment may be completed earlier if the subject does not need the therapy any longer by the investigator's discretion (e.g. cure of the target infection). The therapy may also be discontinued prematurely if the investigator decides that the patient is not capable of receiving further therapy (e.g. adverse event) although the investigator feels that the patient requires further treatment for the condition under study (refer to section 5.8 for discontinuation criteria).

In the event that the additional work-up does not result in a proven or probable IA diagnosis within 7 days of randomization, subjects should continue participation in the trial with possible IA.

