### **5.2.2 Timing of Dose Administration**

MK-5592 will be administered twice a day (12 hours interval) on Day 1 and will be administered every 24 hours on or after Day 2. Voriconazole will be administered twice a day (12 hours interval), however, voriconazole oral tablet should be taken at least one hour before (or at least more than one hour after) a meal.

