### **8.2.11 Extent of Exposure**

The extent to exposure to study treatment will be evaluated by summary statistics (N, mean median, standard deviation) and frequencies for the “Number of Days on Therapy” by treatment group.

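### The all-or-nothing oral day in Section 8.2.10.2, reused in 8.2.11, can make twice-daily voriconazole look less adherent and less exposed than MK-5592 when per-dose adherence is equal

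*Combined protocol and SAP*

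**What the plan says.** Section 8.2.10.2 defines an oral On-Therapy "day if the patient takes the required number of tablets". Percent compliance is the number of such days divided by the number of days the patient should have been on therapy. For a patient followed for the whole period, that denominator "is the total number of days from randomization to the last scheduled day for treatment administration for that patient". For a patient who discontinues, the text offers both an earlier and a later end date without choosing between them. The output is by arm: "Summary statistics will be provided on percent compliance by treatment group for the FAS and ASaT".

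Section 8.2.11 carries the same numerator into exposure: "The extent to exposure to study treatment will be evaluated by summary statistics" and frequencies of the Number of Days on Therapy, by treatment group. It gives no cumulative dose, dose count or first-to-last-dose duration.

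The schedules differ in doses per day. From Day 2, Table 16 gives oral MK-5592 as "300 mg(3 tablets) QD", and Table 18 gives oral voriconazole as "200 mg (4 tablets) BID" before any adjustment from drug monitoring. Section 5.2.2 confirms that MK-5592 "will be administered every 24 hours on or after Day 2". Both drugs are given twice on Day 1. Section 5.2.1.3 states that "the treatment duration of all diseases is 84 days (77-84 days with considering the final treatment allowance").

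**The concern.** A day rule with no partial credit is stricter for a drug taken twice a day than for one taken once. A voriconazole patient who takes one of two doses has received half the day's drug but is scored as untreated. An MK-5592 patient who misses the single daily dose really has had a day without drug. At the same probability of taking each dose, the rule produces a between-arm difference that comes from the scoring.

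The primary objective is to compare safety between the arms, and these two tables are where a reader would look to see whether the drugs were delivered comparably. As defined, they could suggest that the comparator was delivered less well.

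**Working it through.** The plan states no figure for compliance or days on therapy, so there is nothing to reproduce first.

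**Inputs from the documents.** Length T = 84 days (Section 5.2.1.3). Oral MK-5592: 2 doses on Day 1, then 1 a day, so 2 + 83 = 85 doses (Table 16). Oral voriconazole: 2 doses every day, so 168 doses (Table 18). A day scores 1 only if all its doses are taken (Section 8.2.10.2).

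**Assumption.** Per-dose adherence p is the same in both arms. The documents give no value, so a range is shown.

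**Independent misses.** Expected On-Therapy days are:
- MK-5592: p² + 83p
- Voriconazole: 84p²

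At p = 0.95, MK-5592 scores 0.9025 + 78.85 = 79.75 days (94.9%) and voriconazole 84 × 0.9025 = 75.81 days (90.3%). The gap is 3.94 days, or 4.69 points.

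| p | MK-5592 days | Voriconazole days | Gap (days) | Gap (points) |
|---|---|---|---|---|
| 0.99 | 83.15 | 82.33 | 0.82 | 0.98 |
| 0.98 | 82.30 | 80.67 | 1.63 | 1.94 |
| 0.95 | 79.75 | 75.81 | 3.94 | 4.69 |
| 0.90 | 75.51 | 68.04 | 7.47 | 8.89 |
| 0.80 | 67.04 | 53.76 | 13.28 | 15.81 |

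At 77 days and p = 0.95 the gap is 3.61 days, again 4.69 points.

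**Clustering of misses, p = 0.95.**
- Both daily doses always missed together: voriconazole scores 84 × 0.95 = 79.8 days, and the gap is about 0.
- Misses never on the same day: voriconazole scores 84 × (2 × 0.95 − 1) = 75.6 days and MK-5592 0.90 + 78.85 = 79.75 days. The gap is 4.15 days.

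**One patient.** Eight voriconazole doses missed on eight separate days score 76/84 = 90.5% by the day rule, against 160/168 = 95.2% of doses taken. One MK-5592 dose missed after Day 1 scores 83/84 = 98.8% by the day rule and 84/85 = 98.8% by doses, so the two measures agree for that arm.

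**Candidate replacements, p = 0.95.**
- Taken over prescribed: expected value p in both arms, 95.0% against 95.0%. The gap disappears.
- A day counted if any dose is taken: voriconazole 1 − 0.05² = 99.75%, MK-5592 (83 × 0.95 + 0.9975)/84 = 95.1%. The bias reverses at about the same size.

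**Denominator.** Footnote 12 of the Trial Flow Chart allows allocation on Day -1. Counting from that day to Day 84 gives 85 days, so perfect dosing scores 84/85 = 98.8%. This applies to both arms.

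**The case against.** The strongest reply is that these are two descriptive tables. Section 8.2.5.2 analyses safety as the percentage of patients with an event, and Section 8.2.5.1.1 analyses response rates. Neither uses days on therapy, and no exposure-adjusted event rate is planned. That stands. A reader might infer that adverse events will be divided by understated voriconazole exposure, but the plan contains no such calculation.

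The size is also assumed. Patients may miss whole days, in which case the gap vanishes. Not all 84 days are oral and unsupervised: Section 7.1.2.11 requires hospitalisation to Day 9, and Section 5.2.1.1 lets IV starters switch only from Day 9. With independent misses at 95%, each oral day with a two-against-one dose schedule contributes p(1 − p) = 0.0475 day, so the 76 days from Day 9 to Day 84 would give 76 × 0.0475 = 3.61 days. This lowers the figure but leaves the mechanism intact.

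Full-day adherence is also a legitimate description, since a twice-daily day with one dose is not a fully compliant day. That is fair for a figure labelled as such. It does not make the count a suitable sole measure of exposure across two different schedules.

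Two further inferences are tempting and not supported:
- The missed-dose windows (6 hours for voriconazole tablets, 12 hours for MK-5592 tablets) might look like a second source of bias. Each is half its own dosing interval, and any real difference in skipping would be a true difference in per-dose adherence.
- The permitted night-time first dose might look like an arm effect. It is allowed in the same terms in both arms, and the required number can be read as what the permitted schedule asks for on that day.

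**Conclusion.** The point holds as a defect in two descriptive by-arm summaries. The rule and the schedules fix the direction: apart from a trivial Day 1 term, the rule never favours voriconazole. The size is not fixed by the documents. At an assumed 95% per dose over 84 oral days it is about 3.9 days (4.7 points) with independent misses, within bounds of about 0 and 4.2 days. It rests on equal per-dose adherence and on the plain reading that a partly dosed day earns nothing, which the plan implies without saying so outright. It covers oral days only, because Section 8.2.10.1 uses the same ratio for IV treatment without defining an on-therapy day.

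The randomisation-based denominator is a separate, smaller flaw of 1.2 points at most for an 84-day course. It arises only when allocation precedes Day 1 and creates no difference between arms.

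A reader should not conclude that the planned safety or efficacy comparison is biased. What is at risk is how well the comparator appears to have been delivered.

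**What to change.** In Section 8.2.10.2, define oral compliance as tablets taken divided by tablets prescribed, using the prescription as adjusted by drug monitoring for voriconazole. Count from the first dose to the last scheduled dose, or to the last actual dose for patients who discontinue. This removes the dose-frequency artefact and the Day -1 effect, and settles the open choice of end date.

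In Section 8.2.11, report first-to-last-dose duration by arm together with doses taken or cumulative dose. Duration alone ignores missed doses within the course, so the second measure is needed. Do not substitute a count of days with any dose taken as the only measure, because it moves the bias to the other arm (99.8% voriconazole against 95.1% MK-5592 at 95%).

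The cost is wording and slightly more derivation work. Tablet counts (Section 8.2.10) and medication diaries (Section 7.1.1.8) are already collected. The new figures will be less directly comparable with any sponsor trials that use the all-or-nothing day. That figure can be kept as a supplementary line, labelled as full-day adherence.
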